- To estimate the overall survival in patients with CRPC

3. Study design

This is an open label study to determine the effect of Alpharadin on the bone marrow microenvironment in patients with CRPC and bone metastases. We will determine the modulation of bone microenvironment as measured by serum, plasma, urine and bone marrow aspirate bone markers. The baseline determination and subsequent assessment of bone-prostate cancer paracrine signaling will be correlated with PSA decline, progression free survival, overall survival and changes in pain indices.

Subjects will be treated with the standard dosing of xofigo (Alpharadin) Ra-223 dichloride 50 kBq (0.0014 mCi)/kg intravenously every 4 weeks for 6 cycles (6 doses total).

For pharmacodynamic effects: tumor/osteoblast/osteoclast along with Ki-67 (proliferation marker), gamma H2AX (DNA double strand breaks), and cleaved PARP. Co-localization by immunohistochemistry for cytokeratin/PSA for tumor cells, BALP for osteoblasts, and TRAP staining for osteoclasts on bone marrow core samples. This will be performed at pre-treatment, week 12 and week 24.

For plasma markers (peripheral blood) indicative of bone formation and degradation this panel will be performed at baseline, week 12, week 16 and week 24: ALP (alkaline phosphatase) BALP* (bone alkaline phosphatase), OPG (osteoprotegerin), RANKL (receptor activator of nuclear factor-B ligand), OPN (osteopontin), OC (osteocalcin), CTX (c-telopeptide-collagen), PINP* (n-terminal propeptide of type 1 procollagen),

Bone secreted factors in the bone marrow aspirate that reflect the status of osteoblasts or osteocytes

1. Alkaline phosphatase--osteoblasts
2. Osteocalcin—both osteoblasts and osteocytes
3. DMP (Dentin matrix acidic phosphoprotein 1)
4. Sclerostin markers of osteocytes

Bone secreted factors that modulate tumor cell activity and tumor cell response to therapies

1. Tenascin—activate integrins
2. Periostin—activate integrins
3. Lumican—active integrins
4. Decorin—binding to EGFR, IGFR, MET, class A scavenger receptor (SR-A)
5. Osteopontin-binding to CD44 and integrins
6. Osteonectin—activate integrins
7. Nidogen-1—activate integrins
8. TGFb-induced protein ig-h3—activate integrins

Urine: NTx (n-terminus cross-linking telopeptide) a marker of osteoclast activity.

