We will then assess selected factors in the blood and bone marrow aspirates of the treated patients and will correlate the factors with changes in serum bone specific alkaline phosphatase levels and objective clinical evidence of response to therapy. Our correlative studies will expand on the use of the bone markers outlined above in developed patient-derived xenografts (PDXs) that mimic the heterogeneity of bone-metastatic CRPC (SEE APPENDIX E FOR EXPERIMENTAL APPROACH AND TIMELINE). Together, our clinical and mouse model studies will be performed with the objective of identifying novel factors, early predictors of response to Alpharadin that would guide in the further development and possible earlier use of

Alpharadin or other novel alpha emitters as a therapy for CRPC. These correlations will be conducted using descriptive statistics.

4. Study Population

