7.2 Evaluations During Study

On-study tests/visits that must occur within a defined time frame will have a standing window of allowance that is equal to +/- 7 days.

	Screening	Every 4 weeks	Week 12 only	Safety FU visit (Week 24)	Long-term Follow-up
Medical History	x ^a				
Physical Exam	x ^a	x		x	
Vital Signs ⁱ	x ^a	x ^e		x	
ECOG PS	x ^a			x	
Weight	x ^a			x	
CBC/ diff. and plt.	x ^a	x ^e		x	
Serum Chemistry	x ^{a, c}	x ^c		x ^c	
Urinalysis					
PT/PTT	x ^a				
PSA	x ^a	x		x	
Testosterone	x ^a			x	
ECG	X ^a				
ECHO ^j	X ^a				
Chest X-ray	x ^b				
Na-Fluoride PET/CT whole body	x ^b			x	
Bone Scan	x ^a				
Monitor Adverse Events	<----->				
Concomitant Medications	<----->				
Bone marrow asp/bx	x ^a		x	x	
Survival Follow-up					x ^d
Optional Procedures					
Blood for Correlative Studies	x			x	
Urine for Correlative Studies	x			x	

a. Within 21 days of registration

- b. Within 6 weeks of registration
- c. Serum chemistries including albumin, alkaline phosphatase, ALT, AST, calcium, LDH, total bilirubin, creatinine, magnesium, phosphate, calcium, electrolytes (sodium, potassium, chloride, CO₂)
- d. Patients will be followed for survival every 6 months after completion of therapy. This may be done by phone call, e-mail, or medical record review.

8. Adverse Event Reporting

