10.1 Analysis sets

Full population:

All enrolled patients will be used for demographic reporting and calculations of the numbers of patients able to complete the planned schedule and be evaluable for serum and bone marrow marker studies.

Evaluable for Serum Markers:

All patients who have usable baseline and at least one post-baseline serum draws will be evaluable for analysis of serum markers.

Evaluable for Bone Marrow Markers:

All patients who have usable baseline and at least one post-baseline bone marrow biopsy will be evaluable for analyses of bone marrow markers.

Toxicity:

All patients who receive a bone marrow biopsy will be evaluable for toxicity.

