10.2 Variables

Overall survival (OS):

OS will be measured as the number of months from enrollment until death. Patients who are alive at the time of database lock will be censored on the date of last contact.

Progression-free survival (PFS):

PFS will be measured as the number of months from enrollment until progression or death, whichever comes first. Patients who are alive and free of progression at their last response evaluation will be censored on that date. Progression will be defined by the standards set forth within PCWG2.

Demographic variables:

Age at enrollment, race, ethnicity, ECOG status, extent of bone disease (< 6, 6-20, >20)

PD Effects:

Tumor/osteoblast/osteoclast, Ki-67, gamma H2AX, cleaved PRP, cytokeratin/PSA, BALP, and TRAP

Serum biomarkers:

ALP, BALP, APG, RANKL, OPN, OC, CTX, PINP

Bone marrow biomarkers:

Alkaline phosphatase, osteocalcin, DMP, sclerostin, tenascin, periostin, lumican, decorin, osteopontin, osteonectin, nidogen-1, TGFb-induced protein ig-h3.

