10.5 Primary Objective Exploration

Each marker will be tested individually using a Cox regression model to determine whether it is associated with overall survival. Markers measured on a continuous or ordinal scale will be included with their original units in the model. First, the baseline values will be used to determine if the baseline is associated with survival. Next we will calculate the percent change from baseline and use that as a continuous measure in the model. The ordered category of reduced by 30%, same, or increased by 30% grouping will be used in the model. Finally, all observed values of the marker will be included as a time-varying covariate in the Cox regression model. Since this is an observational study to identify potential usefulness of biomarkers in predicting overall survival, no formal adjustments for multiple testing will be needed for future trial planning. However, for publication, only markers with a significance level of ≤ 0.002 will be considered meaningful in predicting survival. This is based on a Bonferroni correction of approximately 25 markers of interest. Additional regression-tree style partitioning may be performed to identify potentially meaningful cutpoints for combinations of markers. Cutpoints will be examined together with demographic and medical status variables. This will be purely exploratory and will need to be confirmed in an independent data set in a future trial.

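### Section 3 and the Section 7.2 visit table disagree on when the plasma marker panel is drawn; if the table is followed, seven of eight markers have no blood value between baseline and week 24

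*Combined protocol and SAP*

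**What the plan says.** **Blood panel.** Section 3 names eight plasma markers (ALP, BALP, OPG, RANKL, OPN, OC, CTX, PINP) and states that "this panel will be performed at baseline, week 12, week 16 and week 24". Section 10.2 carries the same eight as serum biomarkers (its list ends "RANKL, OPN, OC, CTX, PINP"; OPG is printed there as APG).

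**Visit table.** In Section 7.2 the row "Blood for Correlative Studies" is marked at screening and at the week-24 safety visit only, in the optional block. The four-weekly cell is blank. A column for week 12 alone exists, but only the marrow procedure is marked in it. There is no week-16 column. Footnote c ("Serum chemistries including albumin, alkaline phosphatase") puts total ALP in the chemistry drawn every four weeks.

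**Marrow.** For the marrow cores Section 3 says "This will be performed at pre-treatment, week 12 and week 24", and the table's marrow row agrees.

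**Analysis.** Section 10.1: "All patients who have usable baseline and at least one post-baseline serum draws will be evaluable for analysis of serum markers". Section 10.5 tests baseline values, percent change and 30% change classes against overall survival, and then "all observed values of the marker will be included as a time-varying covariate in the Cox regression model". Section 3 gives the aim of finding "early predictors of response to Alpharadin".

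**PFS.** Section 10.2 counts progression or death as the event, and censors patients alive and progression-free at their last response evaluation on that date. The 7.2 table has PSA every four weeks and at week 24, NaF PET/CT at screening and week 24, and bone scan at screening. After that it has six-monthly survival contact only. Section 10.6 repeats the marker analyses for PFS.

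**The concern.** Serum markers are part of the primary objective, yet the document gives two incompatible sampling schedules for them. Sites usually work from the visit table, and blood that was not drawn cannot be recovered at analysis. If the table governs, the repeated-measures plan reduces to a before-and-after pair for seven markers, and the after value exists only for patients who reach week 24. Section 3 also plans to correlate marrow and blood factors with change in bone-specific ALP. BALP is one of the seven, so week-12 marrow would have no blood BALP change from the same visit to set against it.

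The PFS wording is a smaller and separate matter. A patient progression-free at week 24 who dies later is an event under one sentence of Section 10.2 and could be read as censored under the next.

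**Working it through.** 1. **The plan's own figure.** Section 10.8 gives 80% power for HR 1.57 at SD 1.25 with 25 patients. Events = (1.96 + 0.84)² / (SD² × (ln HR)²) = 7.84 / (1.5625 × 0.2035) = 24.7, so it reproduces if all 25 patients die. It does not involve the draw schedule, and this point does not rest on it.

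2. **The schedules side by side.**

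| Time | Section 3 panel | 7.2 correlative blood | 7.2 chemistry (total ALP) | 7.2 marrow |
|---|---|---|---|---|
| Baseline | yes | yes | yes | yes |
| Week 12 | yes | no | yes | yes |
| Week 16 | yes | no | yes | not planned |
| Week 24 | yes | yes | yes | yes |

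The marrow row falls where Section 3 puts it, so a shifted column is an unlikely explanation for the blood row.

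3. **Count.** Planned post-baseline marker-times: 8 × 3 = 24. Total ALP is covered by chemistry, leaving 8 − 1 = 7 markers. Not marked: 7 × 2 = 14, and 14/24 = 58%.

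4. **Effect on each analysis, if the table is followed.**
   - Serum evaluability (10.1) for the seven markers needs the week-24 draw.
   - Percent change and the 30% classes (10.5) exist at week 24 only.
   - The time-varying Cox model has one update. Deaths before week 24 are analysed at the baseline value.
   - Unaffected: baseline models, total ALP, and marrow markers at week 12.

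5. **Patients affected.** The documents give no survival curve for this cohort. I assume the 14.9-month median quoted in Section 1.4 for the phase III radium-223 arm, with Weibull shape k: dead by t = 1 − 0.5^((t/14.9)^k). Week 12 is 2.76 months and week 24 is 5.52 months.

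| k | Dead by week 12 | Dead by week 24 | Difference × 25 |
|---|---|---|---|
| 1 (exponential) | 12.0% | 22.6% | 2.6 |
| 1.25 | 8.1% | 18.2% | 2.5 |
| 1.5 | 5.4% | 14.5% | 2.3 |
| 2 | 2.3% | 9.1% | 1.7 |

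An illness-death simulation tuned to the same median (progression median 4 to 10 months, death without progression 0.005 to 0.02 per month, all assumed) gives 2.3 to 2.5. So about 2 to 3 more patients would die without any post-baseline value than if week 12 were drawn. Other dropout and refusal of an optional draw would add to this; the documents give no rate.

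6. **Power.** Losing 2 to 3 of 25 patients from the change analyses costs little. I give no detectable hazard ratio. It would need the SD of percent change, which is not stated, and the number of deaths at analysis, which depends on whether 90% deaths or the two-year limit comes first.

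7. **PFS.** Assume progression median m and death without progression of 0.01 per month. Then progression-free patients at week 24 number 25 × exp(−(ln 2/m + 0.01) × 5.52), which is 9.1 for m = 4 and 16.1 for m = 10 months. To see the direction of bias I simulated m = 10 with median OS 14.9 months and 12 months' accrual, counting later deaths as events but missing later progressions. PFS at 18 months is 0.38 if survivors stay at risk and 0.32 if they are censored back at week 24, against a true 0.24. At 30 months the censored-back curve reads 0.06 against a true 0.09.

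**The case against.** The best reply is that the table simply omits the draws. Section 3 states the schedule outright, and Section 10.4 says that markers are measured repeatedly. The supplied text is also incomplete: the table carries marks for footnotes e, i and j whose text is absent, and the Appendix 1 cited in Section 7.1 is not included, so collection detail there cannot be checked. That stands as a caution. The blood row carries no footnote mark, however, and a correct appendix would still leave the table contradicting Section 3.

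It is also fair that the study is described as observational and preliminary, that optional sampling may be a deliberate consent choice, and that the patient counts above rest on assumed curves. For these reasons the fix asks the sponsor to state whether the draw is optional, and does not presume the answer.

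Three stronger readings are tempting and are not supported:
- That the week-12 and week-16 samples will not be taken. The documents conflict; they do not settle which schedule sites will use.
- That PFS follow-up ends at week 24. Section 10.2 censors at the last response evaluation without limiting this to evaluations in the table, and follow-up may already use record review.
- That PFS is simply biased upward. Missed progressions push the curve up, censoring survivors back at week 24 pulls it down, and the net effect changes with time.

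**Conclusion.** The schedule conflict is an error as written and should be corrected. Its size is conditional on the table being followed: seven of eight blood markers would lose both intermediate values (58% of post-baseline marker-times), and the aim of early predictors could not be met in blood for those seven. The extra 2 to 3 of 25 patients without a post-baseline value depend on the assumed 14.9-month median and curve shape. The principal loss is the early measurements themselves; the power cost is minor, and overall survival as an outcome is untouched.

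The PFS point is real but minor. Section 10.2 leaves open which evaluations count and how a later death is treated. The share of patients it touches depends on progression rates that the documents do not give.

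**What to change.** **Blood panel.** Reconcile Section 3 with the 7.2 table.
- If the Section 3 schedule stands, mark correlative blood at the existing week-12 and week-16 visits (week 16 needs a column or a footnote to the four-weekly column), and state whether a sample needed for the primary objective is optional.
- If the table stands, limit Sections 3 and 10.5 to baseline and week 24 for BALP, OPG, RANKL, OPN, OC, CTX and PINP, and drop the claim to early blood predictors for them.

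The first option costs one table row and a column or footnote, plus sample processing and assays. Both visits already include a blood draw.

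**PFS.** State one rule in Section 10.2, including how deaths after week 24 count. Either censor at the last date on which progression status was known, and record the progression date at the existing six-monthly contact or record review; or restrict PFS to week 24. The first adds a field to the follow-up form and relies on less standardised dates; the second gives up later PFS.

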4.1 Inclusion criteria

1. Histologically proven adenocarcinoma of the prostate with evidence for skeletal metastases on bone scan and/or CT scan.
2. Eastern Cooperative Oncology Group (ECOG) performance status < 2. (Karnofsky Performance Status $\geq 50\%$)
3. Serum testosterone levels $< 50\text{ng/ml}$
4. Ongoing gonadal androgen deprivation therapy with LHRH analogues or orchiectomy. Patients, who have not had an orchiectomy, must be maintained on standard dosing of LHRH analogue therapy at appropriate frequency for the duration of the study
5. Life expectancy of at least 12 weeks (3 months).
6. Discontinue any steroids prescribed to specifically treat prostate cancer (for e.g as a secondary hormonal manipulation or for cord compression) > 4 weeks prior to study drug. Steroids chronically prescribed for a non-cancer-related illness (e.g. asthma or COPD) that is well controlled with medical management are permissible to an equivalent of < 10 mg Prednisone daily. Note: Steroids may be administered during the study as supportive care.
7. Laboratory Requirements:
 - a. WBC count $> 3,000/\mu\text{l}$
 - b. Absolute Neutrophil Count (ANC) $> 1,500/\mu\text{l}$
 - c. Hemoglobin $\geq 8.0 \text{ g/dL}$ independent of transfusion
 - d. Platelet count $\geq 100,000/\mu\text{L}$
 - e. Serum albumin $\geq 3.0 \text{ g/dL}$
 - f. Calculated or measured creatinine clearance $> 30 \text{ mL/min}$
8. All acute toxic effects of any prior treatment have resolved to NCI-CTCAE v4.0 Grade 1 or less at the time of signing the Informed Consent Form (ICF).
9. Patient must be willing and able to comply with protocol requirements. All patients must sign an informed consent indicating that they are aware of the investigational nature of this study.
10. Patients must also have signed an authorization for the release of their protected health information.

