1.1 Hormone-refractory Prostate Cancer

Prostate cancer has high global incidence and mortality. Approximately one in every nine men in North America will be diagnosed with prostate cancer during his lifetime. It is the most common malignancy and the second most common cause of cancer death in North American males. Worldwide, prostate cancer ranks third in cancer incidence and sixth in cancer mortality among men (1).

The course of prostate cancer from diagnosis to death is categorized as a series of clinical states defined by the extent of disease, hormonal status, and absence or presence of detectable metastases on an imaging study. The states are localized disease, rising prostate specific antigen (PSA) after local therapy with radiation therapy or surgery, advanced disease with clinical metastases that initially respond to androgen ablation therapy, and advanced disease that progresses in the presence of androgen deprivation. PSA is a widely used marker of disease progression and response to treatment changes in PSA foretell subsequent changes in radiographic evidence of metastases. The states are recognized by patients and physicians and allow a clear definition of therapeutic objectives and outcomes.

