Most common hematologic adverse events all grades were anemia (31.2%), neutropenia (5%) and thrombocytopenia (11.5%). Most common non-hematologic all grades adverse events occurring in more than 15% of patients were: bone pain, diarrhea, nausea, vomiting and constipation.

Table 1 shows adverse reactions occurring in $\geq 1\%$ of patients and for which the rate for Ra-223 dichloride exceeds the rate for placebo.

System/Organ Class Preferred Term	Ra-223 dichloride (n=600)		Placebo (n=301)	
	All Grades %	Grades 3-4 %	All Grades %	Grades 3-4 %
Blood and lymphatic system disorders				
Thrombocytopenia	11.5	6.3	5.6	2
Neutropenia	5	2.2	1	0.7
Leukopenia	4.2	1.3	0.3	0.3
Pancytopenia	2	1.2	0	0
Gastrointestinal disorders				
Diarrhea	25	1.5 (grade 3 only)	15	1.7 (grade 3 only)
Vomiting	18.5	1.7 (grade 3 only)	13.6	2.3 (grade 3 only)
Nausea	35.5	1.7 (grade 3 only)	34.6	1.7 (grade 3 only)
General disorders and administration site conditions				
Injection site reactions (including erythema, pain and swelling)	1.2	0	0	0

*Adverse reactions are identified using MedDRA version 14.1 and graded according to CTCAE version 3.0.

*An additional clinically important adverse reaction observed in less than 1% of <PTN>-treated patients and at a higher incidence than in placebo-treated patients was lymphopenia (0.8% vs. 0.3%).

Secondary Malignant Neoplasms

No cases of radiation-induced cancer have been reported in reported in clinical trials with radium-223 dichloride in follow-up of up to three years. However, the radiation dose resulting from therapeutic exposure may result in higher incidence of cancer (e.g. sarcomas of the bone, or leukemia), mutations and a potential for development of hereditary defects.

2. Study objectives

Primary Objective:

- To identify markers of both predictive and prognostic importance within bone marrow biopsies, aspirates as well as serum in patients with metastatic CRPC to bone, to be treated with the standard 6 doses of Alpharadin.

[figure not shown]
Secondary Objectives:

- Link PSA initial concentration (as defined within PCWG2) to modulation of bone markers, in the blood, urine and bone marrow plasma of study patients
- Estimate the efficacy and PFS by PCWG2 in study patients
- Develop a deeply annotated tissue repository for later hypothesis generating associations
- Correlative studies in prostate cancer patient-derived mouse models to validate predictive and prognostic biomarker associations (SEE APPENDIX E)

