11.1 Registration Procedure and Data Reporting

All data will be entered to the Department of Genitourinary Medical Oncology Oracle database (GURU). GURU is a password protected database with an audit trail. Data can be collated with a unique GURU identification in order to de-link information. The minimum required fields will be entered to the MDACC required data collection systems (CORe/PDMS). Registration data entry will occur prior to initiation of therapy. All eligibility criteria must be satisfied. Reporting to the supporting agency will follow the contract agreement.

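### The CRPC population named in the objectives is not carried into the entry criteria: section 4.1 does not require progression under castration, and its testosterone limit as written cannot verify castration

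*Combined protocol and SAP*

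**What the plan says.** **Population intended.** The primary objective in section 2 concerns markers "in patients with metastatic CRPC to bone, to be treated with the standard 6 doses of Alpharadin". Section 3 describes the study as one of the "bone marrow microenvironment in patients with CRPC and bone metastases". Section 1.1, on hormone-refractory disease, gives the last clinical state as "advanced disease that progresses in the presence of androgen deprivation".

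**Population admitted.** Three inclusion criteria in section 4.1 bear on disease state:

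- Criterion 1: "Histologically proven adenocarcinoma of the prostate with evidence for skeletal metastases on bone scan and/or CT scan".
- Criterion 3: "Serum testosterone levels" below 50 ng/ml.
- Criterion 4: "Ongoing gonadal androgen deprivation therapy with LHRH analogues or orchiectomy", with LHRH analogue therapy kept up during the study for men without orchiectomy.

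**Gate.** Section 11.1 says of registration: "All eligibility criteria must be satisfied".

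**Analysis.** Section 10.5 tests each marker on its own in a Cox model for overall survival. The baseline variables listed in 10.2 are age, race, ethnicity, ECOG status and extent of bone disease. Castration-resistance status is not among them. PCWG2 is cited for initial PSA (section 2) and for progression in PFS (sections 2 and 10.2), not for entry.

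**The concern.** The objectives and the entry list describe different populations. The objectives concern men whose disease has escaped castration. The list admits men who are receiving castration therapy, whether or not it is still working.

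This matters because the primary analysis looks for markers associated with survival in 25 patients. Section 1.2 puts one to several years of response to androgen deprivation before the later phase, whose median survival it gives as under two years. A responding man is therefore at an earlier point in the disease. If his marker levels also differ, a single-marker model can attribute to the marker what belongs to disease state. He may also be less likely to die before the analysis, and deaths carry the information in these models.

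The testosterone criterion might have been expected to confirm at least that castration is effective. At the limit and unit written, it does not appear able to.

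**Working it through.** **1. Search for a resistance requirement.** The ten inclusion and fourteen exclusion items, the screening procedures (7.1), the schedule (7.2) and registration (11.1) were read for any requirement of castration resistance, rising PSA, radiographic or bone-scan progression, failure of androgen deprivation, or minimum time on it. There is none. Inclusion 6 mentions secondary hormonal manipulation, but only as one reason for past steroid use. Section 7.1 times the screening CT relative to the start of hormonal ablation, which fits poorly with men who have already progressed on it.

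**2. A test case.** Take a man with bone metastases who recently started an LHRH analogue and is responding.

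- Criterion 1: met.
- Criterion 3: met.
- Criterion 4: met.
- No other item asks about response or progression, so nothing in the list turns on his disease state.

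**3. The testosterone limit.** Input: 50 ng/ml (criterion 3). Conversion: 1 ng/ml = 100 ng/dl, so 50 × 100 = 5,000 ng/dl. The documents give no reference range; 2 to 15 ng/ml is assumed here for non-castrate men.

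| Assumed non-castrate value (ng/ml) | Limit ÷ value |
|---|---|
| 2 | 50/2 = 25 |
| 3 | 50/3 = 16.7 |
| 5 | 50/5 = 10 |
| 10 | 50/10 = 5 |
| 12 | 50/12 = 4.2 |
| 15 | 50/15 = 3.3 |

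At every value tested a non-castrate man passes criterion 3. The same number in ng/dl would be 0.5 ng/ml, so the two units differ 100-fold.

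**4. Slack in the number of deaths.** The figures in 10.8 were reproduced first, using the events formula for a continuous covariate in a Cox model:

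D = (z₀.₉₇₅ + z₀.₈₀)² / (SD² × (ln HR)²), with (1.960 + 0.842)² = 7.849.

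- HR 1.57, SD 1.25: 7.849 / (1.5625 × 0.2035) = 24.7, so 25 deaths.
- HR 1.45, SD 1.5: 7.849 / (2.25 × 0.1381) = 25.3, so 26 deaths (power 79.6% at 25).

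The stated 80% power therefore corresponds to about 25 deaths in 25 patients. With fewer deaths D, power = Φ(√D × SD × ln HR − 1.960), where SD × ln HR = 1.25 × 0.4511 = 0.5638:

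- D = 25: Φ(5.000 × 0.5638 − 1.960) = 80%.
- D = 22: Φ(4.690 × 0.5638 − 1.960) = 75%.
- D = 20: Φ(4.472 × 0.5638 − 1.960) = 71%.

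These show how sensitive power is to lost deaths. They do not forecast how many deaths this gap would cost.

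**5. What cannot be computed.** The documents give neither the likely number of responding men nor their survival. Each one would be 1/25 = 4% of the sample; no more can be said about size.

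**The case against.** The strongest reply is that the intended population is not in doubt. CRPC is named in the primary objective, the overall-survival objective and the design statement. Section 1.2 describes the drug as approved for metastatic castrate-resistant disease. Exclusion 10 lets the investigator refuse unsuitable subjects. All findings are declared preliminary, and 10.5 allows cutpoints to be examined alongside medical status variables. On this view the gap is a drafting omission, and the unit is probably a slip.

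Much of this stands. It lowers the chance that a responding man is enrolled. It does not close the gap, because section 11.1 makes the list the gate, investigator discretion is not a criterion, and the single-marker models are unadjusted.

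Four stronger readings are tempting, and the documents do not support them:

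- A reader might infer that the list admits men who are not being castrated at all. It does not. Criterion 4 requires ongoing LHRH analogue therapy or orchiectomy whatever the testosterone unit. Only criterion 3, taken alone, fails nobody. The exposed group is men on castration therapy who are still responding or are inadequately suppressed.
- A reader might infer that the sample will contain several hormone-sensitive men and that false associations will follow. Nothing gives their number, so the most that can be said is that confounding could occur.
- A reader might infer that such men would mostly be censored at two years. The survival paragraph under 10.4 sets the analysis at 90% deaths or two years after the last patient completes treatment, whichever comes first. Under the time rule, six 4-weekly doses span 5 × 4 = 20 weeks, so a patient completing treatment has potential follow-up of about 2 + 20/52 = 2.4 years, and early enrollees have more. Section 1.2 gives duration of response, not survival, so no censoring fraction follows.
- A reader might infer that screening PSA already makes progression assessable at no cost. Section 7.1 provides one screening value, and one value does not show progression.

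**Conclusion.** The concern holds in this form: section 4.1 selects men under castration therapy but not men resistant to it, and criterion 3 as written cannot verify that castration is effective. The missing resistance requirement is shown by the documents alone. The statement about criterion 3 rests on the assumed non-castrate range of 2 to 15 ng/ml, over which the limit is 3.3 to 25 times too high to fail anyone.

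The effect on results is a possibility of unmeasured size: confounding of the unadjusted overall-survival models by disease state, and loss of deaths from a power statement that leaves none to spare. The text should be corrected because it governs entry. The gap is not evidence that a mixed population was or will be enrolled.

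**What to change.** 1. Confirm the intended testosterone unit and correct criterion 3 so that it can fail a non-castrate patient. The threshold is for the sponsor to settle; none is proposed here.
2. Reconcile 4.1 with the stated population by adding an explicit castration-resistance requirement. The definition is the sponsor's choice. The PCWG2 standard that the protocol already uses for progression is one candidate, but its content is not in the documents, so its suitability for entry could not be checked here.
3. Reconcile the screening CT timing in 7.1 with a population already on androgen deprivation.

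The cost is a short amendment to the text. Testosterone is already measured at screening. The one added burden is that sites must document earlier PSA values or imaging to show progression. No change to dosing or to the analysis models is needed.
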